6.1.3 Screening

Screening: the RA or PI or evaluate each potential patient subject to determine eligibility before the study is described.

6.1.4 Enrollment/Baseline

Enrollment/Baseline Visit (Visit 1, Day 0)

- Obtain informed consent of potential participant verified by signature on study informed consent form or on the REDCap electronic consent form.
- Verify inclusion/exclusion criteria.
- Obtain demographic and clinical information
- Collect baseline data (surveys, fingerstick lipids, six-minute walk test, waist circumference, body mass index)

6.1.5 Final Study Visit

Final Study Visit (Visit 2; 3 months after baseline visit +/- 2 weeks)

- Record adverse events as reported by participant or observed by investigator.
- Collect follow-up data (surveys, fingerstick lipids, six-minute walk test, waist circumference, body mass index)

6.1.6 Withdrawal/Early Termination Visit

If the patient subject terminates the study early and is willing to participate, the PI will collect follow-up data if the patient subject has completed at least 2.5 months of follow-up.

7 Assessment of Safety

7.1 Specification of Safety Parameters

Patient subjects will be counseled on PA by their cardiologist. If they experience any adverse events (for example transient or new chest discomfort) they will be instructed to call their cardiologists immediately. If they experience a severe adverse event (chest discomfort that does not go away or last longer than usual), they will be instructed to activate the emergency response system. The cardiologists will counsel the patients on PA and to monitor for any adverse events during PA.

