Participant Duration	Each participant will be in the study for 3 months. Baseline data collection is at Time 1; followed wearing the Fitbit for 3 months; and follow-up data collection at Time 2 (3 months).

CONFIDENTIAL

This material is the property of the NYU School of Medicine and Langone Medical Center. Do not disclose or use except as authorized in writing by the study sponsor

Interventional Template Version: 11 JAN 2019

Population	We will recruit 59 males and females age > 18 being seen in the NYU Langone Center for Prevention of Cardiovascular Disease (4F). Participants have cardiovascular disease or cardiovascular disease risk factors.
Study Site	NYU Langone Center for Prevention of Cardiovascular Disease (4F)
Number of participants	59 participants in one site
Description of Study Agent/Procedure	The intervention consists of physical activity assessment promotion and remote home step-count monitoring in a clinical cardiology center.
Reference Therapy	This is a one-group study. There is no comparison group.
Key Procedures	Key procedures include assessment of physical activity; counseling by the cardiologist if physical activity levels are <50% of recommended; remote home monitoring via Fitbit sync to MyChart.
Statistical Analysis	Paired t-tests will be used to assess changes in average PA from week 2 to three-month follow-up using PAVS and Fitbit Zip data. Paired t-tests will be used to assess changes in readiness to change number, the 6MWT, BMI, waist circumference, systolic and diastolic BP, lipids, and Framingham Heart Study Risk Score. To assess meaningful improvement in CRF, we will report the percent of participants who achieve a clinically important difference of 25 meters in the 6MWT. Bivariate analyses will compare all CVD risk factors, as well as other potential confounders (e.g. age, sex, race/ethnicity, depressive symptoms, comorbidities), between those who achieve PA recommendations and those who do not. Preliminary effect sizes of change in PA (step counts) will be generated following the Physical Activity Change Detection (PACD) approach. Aim 2 is to conduct a process evaluation of the intervention. Implementation data will be evaluated using the PRISM framework.

CONFIDENTIAL

This material is the property of the NYU School of Medicine and Langone Medical Center. Do not disclose or use except as authorized in writing by the study sponsor
Interventional Template Version: 11 January 2019

Flow diagram Single Group

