2.2 Potential Risks & Benefits

2.2.1 Known Potential Risks

Potential risks associated with this research are fatigue from data collection, inconvenience caused by the need to schedule visits, and loss of confidentiality. There are also inherent risks to participating in physical activity. This will be minimized with the appropriate clinical judgement of the physician in the physical activity promotion process. There is a slight risk of loss of confidentiality in the data collection from the electronic health record, but this will be minimized

CONFIDENTIAL

This material is the property of the NYU School of Medicine and Langone Medical Center. Do not disclose or use except as authorized in writing by the study sponsor
Interventional Template Version: 11 January 2019

by the collection of de-identified data only. There are some risks during the fingerstick blood collection of lipids and glucose. With respect to fingerstick blood collection in general (requiring a small sample size of 40 μ L of blood), some participants may experience temporary discomfort. Some may bruise. Extremely rare risks associated with a fingerstick are bleeding, feeling lightheaded, hematoma, or infection. This risk will be minimized by following established hospital protocols for fingerstick blood collection.

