7.1.1 Definition of Adverse Events (AE)

An **adverse event** (AE) is any symptom, sign, illness or experience that develops or worsens in severity during the course of the study. Intercurrent illnesses or injuries should be regarded as adverse events. Abnormal results of diagnostic procedures are considered to be adverse events if the abnormality:

- results in study withdrawal
- is associated with a serious adverse event
- is associated with clinical signs or symptoms
- leads to additional treatment or to further diagnostic tests
- is considered by the investigator to be of clinical significance

CONFIDENTIAL

This material is the property of the NYU School of Medicine and Langone Medical Center. Do not disclose or use except as authorized in writing by the study sponsor
Interventional Template Version: 11 January 2019

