7.4.1 Adverse Event Reporting

Protocol for Adverse Events. If a patient participant experiences an adverse event during physical activity (e.g. experiencing a fall or musculoskeletal injury), they will be instructed to contact their physician immediately. If the event is an emergency that requires immediate medical attention (e.g. chest, jaw or arm pain, severe shortness of breath, rapid heart rate) they will be instructed to activate the emergency response system (e.g. call 911). The PI will monitor all reports of adverse events or serious adverse events related to this intervention. In the event an adverse or serious adverse event occurs, this will be reported immediately to the Data Safety Monitoring Board, the NYU IRB and to the sponsoring agency. A thorough investigation will be initiated, including review of the protocol to insure no undue exposure to risk occurred.

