7.4.2 Serious Adverse Event Reporting

The protocol for serious adverse events will follow the same protocol for adverse events. If the event is an emergency that requires immediate medical attention (e.g. chest, jaw or arm pain, severe shortness of breath, rapid heart rate) they will be instructed to activate the emergency response system (e.g. call 911). The PI will monitor all reports of adverse events or serious adverse events related to this intervention. In the event an adverse or serious adverse event occurs, this will be reported immediately to the Data Safety Monitoring Board, the NYU IRB and to the sponsoring agency. A thorough investigation will be initiated, including review of the protocol to insure no undue exposure to risk occurred.

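### Section 7.1's cardiologist-call and emergency tiers overlap for new chest discomfort that is still present, and its emergency tier omits symptoms that 7.4.1 and 7.4.2 list for 911

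*Combined protocol and SAP*

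**What the plan says.** Section 7.1 (Specification of Safety Parameters) has two tiers. The lower one reads: "If they experience any adverse events (for example transient or new chest discomfort) they will be instructed to call their cardiologists immediately". The upper one covers a severe adverse event, which it describes as "chest discomfort that does not go away or last longer than usual", and sends the participant to emergency services. That description is not marked as an example and names no symptom other than chest discomfort.

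Section 7.4.1 (Adverse Event Reporting) also has two tiers. For an "adverse event during physical activity (e.g. experiencing a fall or musculoskeletal injury), they will be instructed to contact their physician immediately". The upper tier begins "If the event is an emergency that requires immediate medical attention (e.g. chest, jaw or arm pain, severe shortness of breath, rapid heart rate" and leads to a 911 call. The chest example there carries no limit on duration or novelty.

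Section 7.4.2 opens with "The protocol for serious adverse events will follow the same protocol for adverse events" and repeats the emergency examples of 7.4.1.

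Section 7.1.1 defines an adverse event broadly, as "any symptom, sign, illness or experience that develops or worsens in severity during the course of the study".

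**The concern.** A participant who feels chest discomfort for the first time, and still feels it, needs one answer to the question of whom to call. The lower tier of 7.1 names new chest discomfort as its only example and answers with the cardiologist. The next sentence of 7.1 may already answer with emergency services. The leading emergency example in 7.4.1 points to 911.

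The population makes the point worth settling. The Protocol Summary states: "Participants have cardiovascular disease or cardiovascular disease risk factors". Under 6.1.1, patients who are not eligible for cardiac rehabilitation, or who do not want it, are advised to begin or step up activity. Monitoring then takes place at home, and the weekly review in 6.1.1 concerns device wear and data syncing, not symptoms. Section 2.2.1 itself says: "There are also inherent risks to participating in physical activity". What is at stake is the clarity of a safety instruction. No estimate or test depends on it.

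**Working it through.** No arithmetic applies. The check sets the tiers side by side for the symptoms they are meant to sort. The rows are illustrations, not a count of failures.

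| Symptom | 7.1, call cardiologist | 7.1, emergency services | 7.4.1 and 7.4.2 |
|---|---|---|---|
| Brief chest discomfort, fully resolved | Fits ('transient') | Does not fit | The physician tier can apply: 7.1.1 makes any symptom that develops an adverse event, and the fall/injury list is illustrative |
| New chest discomfort, just begun and still present | Fits ('new') | Can fit, since it has not gone away; no time is stated | Matches the 911 example if the event is taken as an emergency |
| New chest discomfort that has clearly persisted | Still fits 'new' literally | Fits | 911 |
| Jaw or arm pain, severe breathlessness, rapid heart rate | Falls here by default, as an adverse event | Not listed | Examples for 911 |

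**Step 1: does 'new' widen the call tier?** Yes. It is joined to 'transient' by 'or', so a symptom need not be transient to qualify. A first episode still under way is included.

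**Step 2: does the upper tier of 7.1 remove that symptom from the call tier?** Only once it counts as not going away. The section gives no interval after which that is so. Until then both tiers can be read to apply, and nothing says which takes precedence.

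**Step 3: does the other limb of the upper tier help?** 'Longer than usual' presupposes a usual duration. A patient with a known pattern of chest discomfort has one; a patient in a first episode does not. For that patient only the undefined limb is left.

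**Step 4: do the definitions elsewhere set the boundary?** Section 7.2.1 grades an event as severe by its interruption of daily activity and its potential threat to life. Section 7.1.2 defines serious events by outcome or medical importance. Neither contains a rule on time or on chest symptoms that a participant could act on.

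**Step 5: are the emergency lists the same?** No. The upper tier of 7.1 covers chest discomfort only. Sections 7.4.1 and 7.4.2 add jaw or arm pain, severe shortness of breath and rapid heart rate.

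**The case against.** A reader might infer that 7.1 and 7.4.1 flatly contradict each other. The documents do not support that. The two sections share a structure: an ordinary event goes to the physician and an emergency goes to emergency services. Section 7.4.1 does not send all chest pain to 911; the condition that the event is an emergency governs, and the symptoms only illustrate it. Discomfort still in progress has not gone away, so the second sentence of 7.1 can already give the same answer as 7.4.1. Section 7.1 also speaks of discomfort where 7.4.1 speaks of pain, listed beside severe breathlessness, which may signal a different severity. All of this stands, and it reduces the point from a conflict of rules to an undefined boundary within 7.1 and a mismatch of lists.

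It does not remove the point. Whoever applies the instruction has to decide whether the event is an emergency, and will lean on the examples. The protocol neither defines pain and discomfort separately nor says that they call for different actions.

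It can also be said that the remedy restates 7.1 and leaves a time limit open. That is partly fair: the limit is a clinical judgement and is left to the participating cardiologists. Deleting 'or new' is nevertheless a real change, because a symptom still present would no longer fit the call tier.

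Finally, the exclusions in 5.2 (unstable angina and aortic stenosis among them), cardiologist judgement and the safety board in 7.7 lower the risk. They do not tell a participant whom to call first.

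**Conclusion.** The point holds as a minor defect of wording. In 7.1 the two tiers overlap for new chest discomfort that is still present, because no time boundary is given and 'longer than usual' does not work for a first episode. The emergency tier of 7.1 is also narrower than the examples in 7.4.1 and 7.4.2.

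No size can be put on it. The documents give no rate of chest symptoms in this population, so no number of affected participants is claimed. No endpoint, power calculation or analysis changes.

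A reader might go further and infer that participants have been misdirected or that care would be delayed. The documents do not show this. The consent pages are not part of the reviewed text, so the wording participants receive is unknown, and 7.1 leaves counselling on activity and symptoms to the cardiologists, who may already give a clear rule. The verdict rests on the protocol text alone and on reading 'new' as an alternative to 'transient'.

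**What to change.** Amend 7.1, 7.4.1 and 7.4.2 to carry one rule:

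- **Call tier.** Limit it to brief chest symptoms that have fully resolved: stop activity and call the cardiologist at once. Delete 'or new' from 7.1.
- **Emergency tier.** Chest, jaw or arm pain or discomfort still present after stopping activity means 911 first. The participating cardiologists set the time limit, and the text states it.
- **First episodes.** Drop 'longer than usual' as a trigger.
- **Symptom list.** Use the 7.4.1 emergency list, including severe shortness of breath and rapid heart rate, in all three sections.
- **Participant instruction.** Compare it with the amended text and align it if it differs, re-issuing it to those already enrolled.

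The cost is a short amendment, re-issue of the instruction if it needs changing, and possibly a few more emergency calls. No added staff, visits or data are needed.

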7.1.1 Definition of Adverse Events (AE)

An **adverse event** (AE) is any symptom, sign, illness or experience that develops or worsens in severity during the course of the study. Intercurrent illnesses or injuries should be regarded as adverse events. Abnormal results of diagnostic procedures are considered to be adverse events if the abnormality:

- results in study withdrawal
- is associated with a serious adverse event
- is associated with clinical signs or symptoms
- leads to additional treatment or to further diagnostic tests
- is considered by the investigator to be of clinical significance

CONFIDENTIAL

This material is the property of the NYU School of Medicine and Langone Medical Center. Do not disclose or use except as authorized in writing by the study sponsor
Interventional Template Version: 11 January 2019

7.1.2 Definition of Serious Adverse Events (SAE)

Serious Adverse Event

Adverse events are classified as serious or non-serious. A **serious adverse event** is any AE that is:

- fatal
- life-threatening
- requires or prolongs hospital stay
- results in persistent or significant disability or incapacity
- an important medical event

Important medical events are those that may not be immediately life threatening, but are clearly of major clinical significance. They may jeopardize the subject, and may require intervention to prevent one of the other serious outcomes noted above. For example, drug overdose or abuse, a seizure that did not result in in-patient hospitalization, or intensive treatment of bronchospasm in an emergency department would typically be considered serious.

All adverse events that do not meet any of the criteria for serious should be regarded as **non-serious adverse events**.

7.1.3 Definition of Unanticipated Problems (UP)

Unanticipated Problems Involving Risk to Subjects or Others

Any incident, experience, or outcome that meets all of the following criteria:

- Unexpected in nature, severity, or frequency (i.e. not described in study-related documents such as the IRB-approved protocol or consent form, the investigators brochure, etc)
- Related or possibly related to participation in the research (i.e. possibly related means there is a reasonable possibility that the incident experience, or outcome may have been caused by the procedures involved in the research)
- Suggests that the research places subjects or others at greater risk of harm (including physical, psychological, economic, or social harm).

7.2 Classification of an Adverse Event

7.2.1 Severity of Event

For AEs not included in the protocol defined grading system, the following guidelines will be used to describe severity.

- **Mild** – Events require minimal or no treatment and do not interfere with the participant's daily activities.
- **Moderate** – Events result in a low level of inconvenience or concern with the therapeutic measures. Moderate events may cause some interference with functioning.
- **Severe** – Events interrupt a participant's usual daily activity and may require systemic drug therapy or other treatment. Severe events are usually potentially life-threatening or incapacitating.

CONFIDENTIAL

This material is the property of the NYU School of Medicine and Langone Medical Center. Do not disclose or use except as authorized in writing by the study sponsor
Interventional Template Version: 11 January 2019

7.2.2 Expectedness

PI [name], in consultation with the DSMB will be responsible for determining whether an AE is expected or unexpected. The patient-subject's cardiologist will also be consulted. An AE will be considered unexpected if the nature, severity, or frequency of the event is not consistent with the risk information previously described for the study agent.

7.3 Time Period and Frequency for Event Assessment and Follow-Up

The occurrence of an AE or SAE may come to the attention of study personnel during study visits and interviews of a study participant presenting for medical care, or upon review by a study monitor. All AEs including local and systemic reactions not meeting the criteria for SAEs will be captured on the appropriate RF. Information to be collected includes event description, time of onset, clinician's assessment of severity, relationship to study product (assessed only by those with the training and authority to make a diagnosis), and time of resolution/stabilization of the event. All AEs occurring while on study must be documented appropriately regardless of relationship. All AEs will be followed to adequate resolution.

Any medical condition that is present at the time that the participant is screened will be considered as baseline and not reported as an AE. However, if the study participant's condition deteriorates at any time during the study, it will be recorded as an AE. UPs will be recorded in the data collection system throughout the study.

Changes in the severity of an AE will be documented to allow an assessment of the duration of the event at each level of severity to be performed. AEs characterized as intermittent require documentation of onset and duration of each episode.

The PI will record all reportable events with start dates occurring any time after informed consent is obtained until 7 (for non-serious AEs) or 30 days (for SAEs) after the last day of study participation. At each study visit, the investigator will inquire about the occurrence of AE/SAEs since the last visit. Events will be followed for outcome information until resolution or stabilization.

All unresolved adverse events should be followed by the investigator until the events are resolved, the subject is lost to follow-up, or the adverse event is otherwise explained. At the last scheduled visit, the investigator should instruct each subject to report any subsequent event(s) that the subject, or the subject's personal physician, believes might reasonably be related to participation in this study. The investigator should notify the study sponsor of any death or adverse event occurring at any time after a subject has discontinued or terminated study participation that may reasonably be related to this study. The sponsor should also be notified if the investigator should become aware of the development of cancer or of a congenital anomaly in a subsequently conceived offspring of a subject that has participated in this study.

